6. STATISTICAL CONSIDERATIONS

This is a pilot study to evaluate pharmacologically-based dosing approaches to prevent the nephrotoxic effects of HDMTX and cisplatin and ototoxic effect of cisplatin in children, adolescents and young adults with osteosarcoma treated with the standard MAP chemotherapy regimen. Acute biomarkers of AKI (KIM-1, NAG, NGAL) and renal function tests (creatinine, cystatin C, FEMg) will be used to assess the incidence and severity of nephrotoxicity after each course of cisplatin (with and without pantoprazole) and HDMTX (infused over 4 and 12 h), and audiograms will be used to measure hearing loss prior to cycles 1-4 and at the end of therapy.

A 2 x 2 factorial, randomized crossover design will allow patients to serve as their own control. Nephrotoxicity data will be analyzed by course for cisplatin and by dose for HDMTX, and ototoxicity data will be analyzed by treatment cycle. All endpoints will be analyzed as continuous variables.

6.1 Statistical Analysis Plan

6.1.1 Primary Endpoints

- **Urinary KIM-1, NAG and NGAL** will be normalized to the urinary creatinine concentration measured in the same urine specimen and expressed as ng/mg Cr. The end of infusion and 7-day post values for each biomarker will be analyzed by course for cisplatin with vs. without pantoprazole and by dose for HDMTX administered as a 4 h vs. 12 h infusion.
- **GFR** will be estimated from serum creatinine and from the cystatin C (see Section 1.3.3) prior to each course of cisplatin and each dose of HDMTX and 7-days post treatment. A decrease in the GFR will reflect toxicity from the immediately preceding course of

Protocol number: CHP12ST051
Amendment number:
Version date: April 2, 2013

cisplatin or dose of HDMTX. Change in GFR will be analyzed by course for cisplatin with vs. without pantoprazole and by dose for HDMTX administered as a 4 h vs. 12 h infusion.

- Change in **FEMg** from pre-dose 1 (day 1 of cycles 1-4) of cisplatin to pre-dose 2 (day 2 of cycles 1-4) of cisplatin and day 7 will be measured for each cycle containing cisplatin (n=4). Change in FEMg will be analyzed by course for cisplatin with vs. without pantoprazole to assess renal tubular toxicity.
- The **urinary MTX concentration** at the end of each HDMTX infusion on cycles 1-4 will be tabulated for the 4 and 12 h infusion durations and compared to the MTX solubility limit for the urine pH to determine whether the solubility limit was exceeded. End infusion urine MTX concentration will also be correlated with simultaneous serum concentration and with the severity of renal toxicity as measured by AKI biomarkers and serum creatinine and serum cystatin C.
- An **audiogram** will be performed prior to Cycles 1, 2, 3 and 4 and at the end of therapy (after cycle 6). The average hearing level (HL) threshold in dB over the frequency range of 4,000-8,000 Hz will be derived separately for each ear from each audiogram. The increase in the average HL threshold in dB from the pre-cycle 1 to pre-cycle 2, from pre-cycle 2 to pre-cycle 3, from pre-cycle 3 to pre-cycle 4, and from pre-cycle 4 to end of therapy audiograms will be derived and this increase in HL threshold will be compared for cisplatin with vs. without pantoprazole.

For each primary endpoint, we will construct separate models for comparison of cisplatin with vs. without pantoprazole and for comparison of the 4 vs. 12 h infusion durations of HDMTX. Linear mixed effects model will be used for this crossover design, including all repeated measures as the outcome, order type and period number as the fixed effects, and a subject level random intercept to account for within-subject correlation (or unstructured correlation matrix for the repeated measures if needed). Appropriate contrasts will be constructed to test for treatment effect. For nephrotoxicity outcomes using AKI biomarkers, little carryover effect is expected. For ototoxicity outcomes, carryover effect is possible, but unlikely to be differential between comparison arms because we randomized the order of treatment. Nevertheless, we will conduct a statistical test for differential carryover effect, acknowledging limited power with this test. If differential carryover is present in the analysis we will only use the data from cycle 1.

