3.3.2 Number of Subjects and Number of Study Sites

This pilot study will be conducted at CHOP. We plan to study 24 subjects. Patients who do not complete 4 cycles of treatment for any reason may be replaced. We may enroll up to 28 subjects in order to have 24 fully evaluable subjects. Based on the number of children with OS seen at CHOP annually, we expect accrual to be complete in 2 to 3 years.

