6.2 Sample Size and Power

The primary endpoints are sensitive urinary biomarkers of AKI and audiograms, and all endpoints are continuous variables. The study is designed to detect a signal sufficient to justify a randomized trial that would be conducted in a cooperative group setting.

Twenty-four patients will be enrolled and data will be analyzed by dose or treatment cycle with patients serving as their own control. Over the past 5 years 57 newly diagnosed patients with osteosarcoma were seen and treated at CHOP. This is an average of 11.5 patients per year, indicating that we can complete accrual to this study in about two years.

Protocol number: CHP12ST051
Amendment number:
Version date: April 2, 2013

- For the analyses of nephrotoxicity using biomarker endpoints of AKI (Urinary KIM-1, NAG and NGAL), data will be analyzed by course or by dose. Each patient will have 2 courses of cisplatin with pantoprazole and 2 courses without pantoprazole. A power calculation was conducted under the framework of a multivariate general linear hypothesis for general linear models, using the Wilks Lambda test with a significance level of 0.05.^{110,111} Because the comparison will be within subject, a larger within-subject correlation will provide greater power for the test. Based on the most conservative assumption that all repeated measures are independent, we will have 80% power to detect a 0.60SD difference for with vs. without pantoprazole. Assuming a moderate correlation of 0.5, we will have 80% power to detect a smaller difference of 0.42SD. Variability (SD) for these biomarkers in children with AKI are not available, but in a healthy adult population,¹¹² the mean value of KIM-1 was 0.228 with a SD of 0.094, so assuming a similar mean and SD for pediatric patients, we will have 80% power to detect a 0.056 difference (about 25% decrease) in the mean KIM-1 value with pantoprazole, assuming independence among repeated measures. We will have 80% power to detect a difference of 0.039 (about 17% decrease) if the correlation is moderate (e.g. 0.5).

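### The plan does not say how the two post-treatment samples per course are modelled for the urinary kidney markers; read literally they are pooled with no sample-time term, and the sizing assumes one value

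*Combined protocol and SAP*

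**What the plan says.** Section 5.1 gives each urinary marker two post-treatment values: days 2 and 7 for each cisplatin course, and 24 hours and day 7 for each methotrexate infusion. Section 6.1.1 carries both into the analysis: "The end of infusion and 7-day post values for each biomarker will be analyzed by course for cisplatin with vs. without pantoprazole". It adds the same by dose for the 4 h versus 12 h methotrexate comparison, calling the early sample end of infusion for both drugs.

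The model paragraph of Section 6.1.1 separates models by endpoint and by drug comparison, not by sample time. The mixed model is described as "including all repeated measures as the outcome, order type and period number as the fixed effects", with a patient random intercept or, if needed, an unstructured correlation matrix. The treatment test is left to suitable contrasts that are not written out.

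Section 6.2 sizes the cisplatin comparison on this basis: "Each patient will have 2 courses of cisplatin with pantoprazole and 2 courses without pantoprazole". For methotrexate it counts eight repeated measures per patient, four for each infusion duration. It does not say which sample time is meant.

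**The concern.** An early sample and a day-7 sample of an acute injury marker need not have the same mean, and treatment need not act equally on both. A model with neither a sample-time term nor a treatment-by-time term has two distinct consequences:

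- The average difference between the two times is left in the residual, so the treatment contrast is tested against too large an error.
- One common treatment effect is estimated, so an effect present at one time is averaged with its absence at the other.

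The study is meant to find a signal that would justify a larger randomized trial. With 24 patients, an acute protective effect could be missed because of how the samples were combined. If the handling stays open until data are seen, the more favourable time could also be chosen afterwards.

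**Working it through.** **1. Reproducing the sizing.** Inputs from Section 6.2: 24 patients as their own controls, "using the Wilks Lambda test with a significance level of 0.05", and two courses per condition. For a one-degree-of-freedom within-patient contrast, Wilks Lambda is the two-sided paired t test (23 df). With m values per condition and within-patient correlation ρ, SE = SD × √[(1 − ρ)(2/m)/24].

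- Cisplatin, m = 2, ρ = 0: SE = √(1/24) = 0.204; 0.60/0.204 = 2.94; power 80.4%. The plan states "we will have 80% power to detect a 0.60SD difference for with vs. without pantoprazole".
- Cisplatin, m = 2, ρ = 0.5: SE = √(0.5/24) = 0.144; 0.42/0.144 = 2.91; power 79.6%. The plan states "Assuming a moderate correlation of 0.5, we will have 80% power to detect a smaller difference of 0.42SD".
- Methotrexate, m = 4: 79.6% at 0.42 SD (ρ = 0) and 80.4% at 0.30 SD (ρ = 0.5), again as stated.

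All four figures reproduce with one value per course or dose. With two values per cisplatin course (m = 4), 0.60 SD at ρ = 0 would have 97.8% power, and the detectable average difference would be 0.42 SD.

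**2. Effect of the planned size at one time only.** Pooling halves the contrast (0.30 or 0.21 SD) and uses m = 4. Power falls from 80.4% to about 51% (ρ = 0) and from 79.6% to about 50% (ρ = 0.5). To keep 80% power, the effect at that one time would have to be 0.84 or 0.60 SD.

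**3. Adding a gap between times.** Let D be the mean difference between the two sample times in SD units. The documents do not give it, so D = 0, 1 and 2 are assumed, with total SD 1 and intraclass correlation 0.3 (also assumed), hence within-patient residual variance 0.7.

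Omitting sample time adds D²/4 to that variance, so the SE ratio is √[1 + D²/(4 × 0.7)]: 1.00, √1.357 = 1.16 and √2.429 = 1.56. Counting the 164 residual degrees of freedom out of 24 × 4 × 2 = 192 values, the added term is multiplied by 192/164 and the ratios become 1.19 and 1.63.

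For a 0.5 SD effect at one time only, with D = 0:

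- At that time alone: SE = √(0.7/24) = 0.171; 0.5/0.171 = 2.93.
- Pooled: SE = √(0.7 × 0.5/24) = 0.121; 0.25/0.121 = 2.07.

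Simulated power for a 0.5 SD effect (24 patients, four courses, two times; patient effects removed, cycle and treatment fitted; simulation error one to two points):

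| Effect and analysis | D = 0 | D = 1 | D = 2 |
|---|---|---|---|
| Both times, no time term | 98% | 96–97% | 81% |
| Both times, time term added | 98% | 98% | 98% |
| One time only, pooled, no time term | about 54% | 31–44% | 8–17% |
| One time only, pooled, time main effect added | about 52% | about 52% | about 52% |
| One time only, analysed at that time | 82–85% | 82–85% | 82–85% |

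The ranges in the third row cover both signs. The lower figure applies when the effect widens the gap between times, the upper when it narrows the gap. A protective effect at the time when the marker is higher narrows it. The 54% and 52% at D = 0 agree within simulation error.

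The last two rows separate the two problems: a time main effect removes the error inflation but not the dilution.

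**The case against.** The strongest reply is that the plan never says both times share one model. The model paragraph is a template for every primary endpoint, including some with one sample per infusion. Section 6.2 uses repeated measures to mean one value per course or dose. The list of fixed effects is shorthand: it omits treatment itself. On this view the sizing shows that pooling was not intended. This stands in part. A reader might infer that the plan commits to pooling, and the documents do not support that; pooling is the literal reading only. But neither separate models, nor a summary value, nor a primary time is stated, so the handling of a primary endpoint is still open.

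A reader might also infer that power for an acute effect is as low as 8%. That needs a 2 SD gap and an effect that widens it, and neither is in the documents. At D = 0 there is no error inflation at all.

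Nor does omitting the time term bias the contrast or create false positives in balanced data. The test becomes conservative: at D = 1, simulated type I error is 2.6% (ρ = 0) and 1.3% (ρ = 0.5).

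Nor are the two times inseparable, since samples are scheduled and labelled by day. Finally, an effect confined to one time is a possibility, not a documented fact: Section 1.3.2.2 describes cisplatin's renal effects as cumulative and only partly reversible. If the effect is equal at both times, pooling with a time term costs no power.

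**Conclusion.** The point holds as an unspecified analysis of a primary endpoint and a mismatch with the sizing. The sizing arithmetic itself is correct for one value per course or dose.

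If the model is run as written, the dilution is the firmer consequence because it does not depend on D: an effect of planned size at one time falls from about 80% to about 50% power. The error inflation does depend on D: none at D = 0, about 16% on the SE at D = 1 and about 56% at D = 2.

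These figures assume complete balanced data, the stated correlations, and two samples of one course no more alike than other samples from the same patient. If within-course correlation were 0.7, pooled power for a one-time effect of planned size would be about 33% (ρ = 0) or 38% (ρ = 0.5). A random intercept alone would then understate the SE, the opposite direction to the inflation above. The unstructured option addresses that correlation but does not supply the missing mean terms.

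**What to change.** In Section 6.1.1, for the urinary markers:

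- Add sample time and treatment-by-time as fixed effects, or fit one model per sample time. A time main effect alone is not enough.
- Report the treatment effect at each time.
- Name in advance the primary time or contrast for each drug comparison.

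In Section 6.2, state that the detectable differences refer to one value per course or dose, and at which time.

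The samples are already planned, so the cost is wording. The downside is two estimates per marker, and less power than a pooled estimate if the effect is the same at both times: in the 0.5 SD example, 82–85% at a single time against 98% averaged. The joint model still allows the averaged contrast to be pre-specified alongside.

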3.2 Randomization

Patients will be randomized to one of 4 treatment arms (see Study Diagram), which will determine the order in which they receive pantoprazole with cisplatin (Cycles 1&2 vs. Cycles 3&4) and the order in which they will receive HDMTX as a 4 or 12 h infusion (Cycles 1&2 vs. Cycles 3&4). A block randomization procedure will be used so that 3 of the first 12 subjects will be randomly assigned to each of the 4 treatment arms (three patient per arm) and 3 of subjects 13 to 24 will be randomly assigned to each of the 4 arms (six patients per arm when enrollment is completed). Subjects who are unable to complete 4 cycles of therapy may be replaced, and the new subject will be placed on the same treatment arm as the subject being replaced.

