- For comparison of HDMTX infusion durations, each patient will have 4 doses with 4 h infusion duration and 4 doses with 12 h infusion duration. Using the Wilks Lambda test with a significance level of 0.05 under the framework of general linear models, with 24 subjects of 8 repeated measures (4 measures with 4 h duration and 4 measures with 12 h duration), we will have 80% power to detect a 0.42SD difference assuming a within-subject correlation of 0, and will detect a 0.30SD difference assuming a correlation of 0.5.
- For the analyses of ototoxicity data (hearing level thresholds from 4 to 8 kHz in dB), treatment cycle will be the analysis unit. Each patient will have 2 cycles with pantoprazole and 2 cycles without pantoprazole. Using the Wilks Lambda test with a significance level of 0.05 under the framework of general linear models, with 24 subjects of 4 repeated measures (2 measures with and 2 measures without pantoprazole), we will have 80% power to detect a 0.60SD difference assuming a within-subject correlation of 0, and will detect a 0.42SD difference assuming a correlation of 0.5. Moreover, if differential carryover is present, we will only use the data from the first two cycles, so that the comparison will be between subjects, with 12 subjects in each comparison group. We will then have 80% power to detect a 1.2SD difference, based on a two-sided, two-sample t test with a significance level of 0.05.

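### Each primary mixed model leaves the other randomised factor unnamed; adding it is free and matters mainly for the HDMTX-day markers and GFR

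*Combined protocol and SAP*

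**What the plan says.** Section 3.2: "Patients will be randomized to one of 4 treatment arms", which set both the order of pantoprazole and the order of the infusion durations. Section 6: "A 2 x 2 factorial, randomized crossover design will allow patients to serve as their own control".

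For the primary endpoints, section 6.1.1 says that "we will construct separate models for comparison of cisplatin with vs. without pantoprazole and for comparison of the 4 vs. 12 h infusion durations". The listed terms are "order type and period number as the fixed effects, and a subject level random intercept", with an unstructured correlation matrix as an alternative if needed. Treatment is to be tested through contrasts. The section does not define *order type*, and it lists neither the other factor nor an interaction between the two.

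The power statements in section 6.2 treat each factor as if it were alone, for example "we will have 80% power to detect a 0.60SD difference for with vs. without pantoprazole" with independent measures.

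**The concern.** Both factors switch between cycles 1-2 and cycles 3-4. In every patient, the block difference for one factor therefore also contains the full change in the other, with opposite signs in different arms. A random intercept removes what is constant within a patient, and this is not constant.

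The protocol supplies a route for such an effect. HDMTX is given on days 22 and 29, after that cycle's cisplatin with or without pantoprazole (section 3.1.3). Section 1.3.2.2 describes cisplatin's renal effects as cumulative, only partly reversible and able to affect HDMTX elimination. If pantoprazole protects the kidney, the HDMTX-day markers and GFR may shift with it.

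Two things are at stake. Left in the residual, the other factor inflates the standard error. If arms become uneven in a crossed pattern (arms 1 and 4 against arms 2 and 3), part of its effect enters the estimate.

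**Working it through.** **Inputs.** There are 24 patients, six per arm (section 3.2). Each condition has two cisplatin courses or four HDMTX doses; alpha is 0.05, power 80% and within-subject correlation ρ is 0 or 0.5 (section 6.2). Arms 1 and 3 receive pantoprazole first; arms 1 and 2 receive the 4 h infusion first (section 6.1.2). The effect δ of the other factor, in SD, is not in the documents. I use 0.42, the pantoprazole difference that section 6.2 claims to detect at ρ = 0.5, and a smaller 0.2. Both are assumptions.

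**Step 1: the plan's own figures.** With k measures per condition, a patient's block difference has variance (2/k)(1−ρ). A two-sided paired t test on 24 differences (23 df) has 80% power at:

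| k | ρ | Recomputed | Stated |
|---|---|---|---|
| 2 | 0 | 0.597 | 0.60 |
| 2 | 0.5 | 0.422 | 0.42 |
| 4 | 0 | 0.422 | 0.42 |
| 4 | 0.5 | 0.299 | 0.30 |

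The figures reproduce. They allow nothing for the other factor.

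**Step 2: HDMTX model, six per arm, random intercept, ρ = 0.5.** The residual variance is 1−ρ = 0.50. The omitted factor sits at ±δ/2 around the patient mean on eight measures. It adds 24 × 8 × (δ/2)² to the residual sum of squares, on about 24 × 7 − 2 = 166 df.
- δ = 0.42: 192 × 0.0441 / 166 = 0.051; SE ratio √(0.551/0.50) = 1.05.
- δ = 0.2: 192 × 0.01 / 166 = 0.012; SE ratio √(0.512/0.50) = 1.01.

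The true spread of the estimate stays at √(0.25/24) = 0.102; only the reported SE grows, to 0.107 at δ = 0.42. With critical value 1.974, power at 0.30 SD goes from Φ((0.30 − 1.974 × 0.102)/0.102) = 0.83 to Φ((0.30 − 1.974 × 0.107)/0.102) = 0.81. Simulation agrees.

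**Step 3: the same comparison as a block contrast.** The variance is (2/4)(1−0.5) = 0.25, and the omitted factor adds δ².
- δ = 0.42: √((0.25 + 0.1764)/0.25) = 1.31.
- δ = 0.2: √((0.25 + 0.04)/0.25) = 1.08.

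Multiplying δ² by 24/22 for the residual df gives 1.33 and 1.08. Power at 0.30 SD falls to 0.576 and 0.753, against 0.801 with the factor in the model. The unstructured-covariance option is expected to behave similarly; it was not simulated.

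**Step 4: bias when arms are uneven.** For the HDMTX estimate, with n1 to n4 patients in arms 1 to 4, bias/δ in absolute value is ½ × |(n1−n2)/(n1+n2) − (n3−n4)/(n3+n4)|. The pantoprazole estimate gives the same shares for these patterns.

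| Arms 1/2/3/4 | Bias/δ | At δ = 0.42 |
|---|---|---|
| 6/6/6/6 | 0 | 0 |
| 5/5/6/6 or 5/6/5/6 | 0 | 0 |
| 5/6/6/6 | ½ × 1/11 = 4.5% | 0.02 SD |
| 5/6/6/5 | ½ × 2/11 = 9.1% | 0.04 SD |
| 4/6/6/4 | ½ × 4/10 = 20% | 0.08 SD |

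In simulation a true HDMTX effect of 0.30 SD is estimated at 0.34 with 5/6/6/5 and 0.38 with 4/6/6/4. Adding the factor restores 0.30 in both.

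**Step 5: cisplatin models.** At cisplatin sampling, the last HDMTX given was none in cycle 1, block 1's duration in cycles 2 and 3, and block 2's in cycle 4. With duration effects of ±δ/2, the block means differ by only δ/4. At δ = 0.42 even the block-contrast form gives √((0.5 + 0.105²)/0.5) = 1.011, about 1%.

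**The case against.** The case for leaving the plan alone is substantial.

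- **Balance.** Randomisation is blocked to six per arm and replacements join the same arm (section 3.2). At balance the omitted effect cancels exactly. This stands, but replacement is optional and total enrolment is capped at 28 (section 3.3.2). Drugs can be held or stopped for toxicity (section 3.1.5), and an intervention can be dropped at the interim look (section 6.3).
- **Little carryover.** Section 6.1.1 expects little for AKI biomarkers, and section 5.1 compares HDMTX markers with pre-infusion values, which would remove a stable shift. This weakens the case for those markers. It does not close it: section 6.1.1 describes analysing post-dose values and lists no baseline term, and GFR is also a primary outcome.
- **Order type.** If it means the four-level arm and is crossed with period, contrasts could separate the factors. The text says neither.

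A reader might infer stronger claims that the documents do not support. One is that 24 patients do the work of 14 in the HDMTX comparison (24 × 0.25/0.426 = 14.1). That belongs to the block contrast; the plan's default is the random intercept. Another is a 16% loss for cisplatin, √((0.5 + 0.1764)/0.5) = 1.16. That ignores the timing in step 5. A third is bias from arms of seven and five completers; the six-per-arm, same-arm replacement rule does not lead there.

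**Conclusion.** The omission is real and its consequences are modest. For HDMTX-day markers and GFR, an assumed effect of 0.42 SD costs about 5% in standard error under the planned random-intercept model. The cost is about 31% only if the analysis amounts to a block contrast. At 0.2 SD the costs are about 1% and 8%.

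The plan as written is not biased at six per arm; the test is merely conservative. Bias needs crossed loss: 0.02 to 0.08 SD at δ = 0.42 for one to four patients lost in the patterns shown, and nothing when the loss is even across the other factor.

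The point is weak for cisplatin-day AKI markers and FEMg, which are sampled on days 1 to 7. It is weaker still for audiograms, since the documents claim no methotrexate effect on hearing. All the sizes scale with δ, which the documents do not give.

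**What to change.** In section 6.1.1:
- Define *order type*, and write out the treatment term in each model.
- In the HDMTX models, add pantoprazole yes/no for that block as a fixed effect.
- In the GFR models, add the most recent exposure to the other factor. Cycle 1 cisplatin precedes any HDMTX, so code that level as none; the period term absorbs it.
- Optionally, do the same in the other cisplatin models.
- Report the interaction descriptively. Both factors switch together, so their product is constant within a patient and the interaction is a between-patient comparison of arms 1 and 4 with arms 2 and 3.

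The cost is one degree of freedom per model, with no new data or patients. The stated power is kept: in the block-contrast form at 0.30 SD it is 0.801 with the extra term, against 0.803 when the other factor has no effect and is left out.

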9.3	Regulatory and ethical considerations	34
9.3.1	Data safety and monitoring plan	34
9.3.2	Risk assessment	34
9.3.3	Potential benefits of trial participation	35
9.3.4	Risk-benefit assessment	35
9.4	Recruitment strategy	35
9.5	Informed consent/assent	35
9.6	Payments to subjects/families	36
10.	PUBLICATION	36
11.	REFERENCES	36
APPENDIX 1	SAMPLE TREATMENT DELIVERY MAP	43
APPENDIX 2	PEDIATRIC NEUROTOXICITY GRADING SCALE	44
APPENDIX 3	PATIENT REPORTED OUTCOME SURVEY	46

Protocol number: CHP12ST051
 Amendment number:
 Version date: April 2,, 2013

ABBREVIATIONS AND DEFINITIONS OF TERMS

Term	Definition
AKI	Acute kidney injury
AUC	Area under the plasma concentration-time curve
Block	Two consecutive treatment cycles (Cycles 1 & 2 or Cycles 3 & 4)
BMP	Basic mineral panel
BSAP	Bone-specific alkaline phosphatase
CBC	Complete blood counts
CL	Clearance
C _{max}	Peak concentration
CMP	Comprehensive mineral panel
COG	Children's Oncology Group
Course	A course of cisplatin is 60 mg/m ² daily x 2 days (total dose 120 mg/m ²); a course of doxorubicin is 37 mg/m ² daily x 2 days (total dose 75 mg/m ²); a course of HDMTX is two 12 g/m ² infusions administered 1 week apart
Cr	Creatinine
CrCL	Creatinine clearance
CR	Complete Response
Cycle	A course of cisplatin and doxorubicin followed 3 weeks later by a course of HDMTX (cycles 1-4; duration 5 weeks); OR A course of doxorubicin followed 2 weeks later by a course of HDMTX (cycles 5&6; duration 4 weeks)
EOI	End of infusion
EOT	End of therapy
FEMg	Fraction excretion of magnesium
GFR	Glomerular filtration rate
H&P	History and physical exam
HDMTX	High-dose methotrexate (12 g/m ²)
IV	Intravenous
KIM-1	Kidney Injury Molecule-1
LV	Leucovorin
MAP	Methotrexate, Adriamycin (doxorubicin), cisPlatin
Mg	Magnesium
MTX	Methotrexate
NAG	N-Acetyl-β-D-Glucosamidase
NGAL	Neutrophil Gelatinase-Associated Lipocalin
OCT2	Organic cation transporter 2
OS	Osteosarcoma
PK	Pharmacokinetics
Pre-op	Preoperatively
PPI	Proton pump inhibitor
PR	Partial Response

Protocol number: CHP12ST051

Amendment number:

Version date: April 2,, 2013

Pre-Rx	Pretreatment
PRO	Patient reported outcome
PS	Performance score (Lansky or Karnofsky)
T _{1/2}	Half-life
TDM	Treatment delivery map (roadmap)
UA	Urinalysis

PROTOCOL SYNOPSIS

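### For hearing, sections 6.1.1 and 6.2 name different fallback data sets after the same carryover test; that test has no stated level or statistic, and the reason given for expecting no differential carryover is invalid.

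*Combined protocol and SAP*

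**What the plan says.** Section 6.1.1 specifies a linear mixed model on all repeated measures, with order and period as fixed effects and a random intercept for each subject. For ototoxicity it says "carryover effect is possible, but unlikely to be differential between comparison arms because we randomized the order of treatment". It continues: "Nevertheless, we will conduct a statistical test for differential carryover effect, acknowledging limited power with this test". The consequence of a positive test is "If differential carryover is present in the analysis we will only use the data from cycle 1".

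Section 6.2, in its paragraph on ototoxicity, gives a different consequence: "if differential carryover is present, we will only use the data from the first two cycles, so that the comparison will be between subjects". The groups are taken to be 12 v 12, and the power statement for this case is "We will then have 80% power to detect a 1.2SD difference", from a two-sided, two-sample t test at 0.05.

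The list of abbreviations and definitions gives a cycle as one five-week unit and a block as "Two consecutive treatment cycles (Cycles 1 & 2 or Cycles 3 & 4". The audiogram paragraph of section 6.1.1 yields one threshold increase per cycle, so cycle 1 supplies one increment per ear and the first two cycles supply two.

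**The concern.** There are three defects.

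- **Conflicting fallback data.** Two analysts following the plan faithfully, one from 6.1.1 and one from 6.2, would analyse different data and could report different conclusions for the same trial.
- **A test on the data chooses the analysis.** If the carryover test statistic is correlated with the fallback comparison, the fallback no longer has a 5% error rate in the trials where it is used. The plan concedes low power for the test but does not mention this selection effect.
- **An invalid reason.** Randomising order makes the two sequence groups comparable at entry. Differential carryover is a difference between what cisplatin with pantoprazole and cisplatin without it leave behind, and randomisation does not remove that.

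Hearing is the endpoint for which the plan itself says carryover is possible, and section 6.2 says the study's signal is meant to justify a randomised trial.

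**Working it through.** **1. The plan's own figures reproduce.** Inputs from section 6.2: 24 patients, two cycles per treatment, two-sided 0.05, 80% power, correlation ρ of 0 or 0.5.

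- Fallback, 12 v 12: noncentrality 1.2 × √(12/2) = 2.94 on 22 df. Power is 80.2% and the detectable difference is 1.197 SD (stated 1.2).
- Crossover: SD of the within-patient contrast = √(2(1−ρ)/2). The detectable difference is 0.597 SD at ρ = 0 (stated 0.60) and 0.422 SD at ρ = 0.5 (stated 0.42).

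The arithmetic is right, but the unit of the 1.2 SD is not stated. On the single-cycle SD scale, a two-cycle mean has SD √((1+ρ)/2). The detectable difference is then 1.197 × 0.707 = 0.85 SD at ρ = 0, or 1.197 × 0.866 = 1.04 SD at ρ = 0.5. So 1.2 fits either cycle 1 alone, or two cycles with the SD taken on the two-cycle change.

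**2. The two fallbacks differ in substance.** At 120 mg/m² per course, cumulative cisplatin is 120 mg/m² after cycle 1 and 240 mg/m² after cycle 2. Section 1.3.4 places initial high-frequency loss at cumulative doses above 300 mg/m². Both fallbacks lie below that dose, and cycle 1 is further below it.

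**3. Effect of the test-then-switch rule.** Assumed, because the plan does not say: carryover test level 5% or 10%, and its statistic. Setting: 12 per sequence, no treatment effect, no carryover, treatment test at 5%.

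*Patient totals, exchangeable measures.* The correlation of the total with cycle 1 is √(1+3ρ)/2 = 0.50 (ρ = 0) or 0.79 (ρ = 0.5). With the block-1 mean it is √((1+3ρ)/(2(1+ρ))) = 0.71 or 0.91. The total is uncorrelated with the crossover contrast, so

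overall error ≈ a × (fallback error given a positive test) + (1 − a) × 5%, where a is the carryover test level.

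Simulation, 400,000 trials per row:

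| ρ | a | Cycle 1: overall (given positive) | Two cycles: overall (given positive) | Fallbacks disagree, given positive |
|---|---|---|---|---|
| 0 | 5% | 5.64% (16.9%) | 6.40% (32.0%) | 26.0% |
| 0 | 10% | 5.92% (13.9%) | 6.94% (24.1%) | 21.1% |
| 0.5 | 5% | 6.80% (40.8%) | 7.78% (60.4%) | 31.7% |
| 0.5 | 10% | 7.48% (29.9%) | 8.61% (41.1%) | 26.2% |

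Check on the last row, two cycles: 0.10 × 41.1% + 0.90 × 5% = 8.6%. Repeat simulations move the conditional figures by a point or two.

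As a share of all null trials, disagreement runs from 0.05 × 26.0% = 1.3% to 0.10 × 26.2% = 2.6%.

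*Patient totals, noise only from audiograms shared by successive increments.* Overall error is 5.6–5.9%. Given a positive test it is about 13–18% for both fallbacks.

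*Within-patient carryover contrast.* Two cycles on each treatment also allow weights (−0.5, 0.5, 1, −1) across the four cycles. With exchangeable measures:

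- Covariance with the block-1 mean is (1−ρ)(−0.25 + 0.25) = 0, so the two-cycle fallback keeps about 5% after a positive test.
- Correlation with cycle 1 is −0.5√(1−ρ)/√2.5 = −0.32 (ρ = 0) or −0.22 (ρ = 0.5), and that fallback has about 7–10%.
- Overall error, with audiogram noise included, is about 5.0–5.6%.

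**The case against.** The strongest reply is that the plan never names the totals statistic. Its mixed model on all four measures would allow a within-patient test, and under exchangeable measures that leaves the two-cycle fallback close to 5%. This stands: the large conditional rates belong to one possible reading of the plan. The concession of limited power may suggest the totals test, but nothing settles it.

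A second reply is that cycle 1 is probably a slip for the first block. Section 6.2 is the fuller statement and fits the design's period. That is plausible, but the protocol defines the two terms separately, and 6.1.1 is the section an analyst would follow.

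A third is that this is a pilot and the overall inflation is modest. That is true, and it limits the weight of the point. It does not remove a contradiction in a primary-endpoint analysis.

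Three stronger readings are tempting, and the documents do not support them:

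- *A reader might infer that differential carryover is present and biases the hearing result.* No document gives its existence or size. Simple cumulative-dose models that were tried gave none, in which case every positive test would be a chance finding.
- *A reader might infer that 12 per group cannot be reached, since patients with baseline hearing loss may enrol.* Section 3.1 plans 24 evaluable patients, and section 3.3.2 allows up to 28 to obtain 24 fully evaluable. Whether that covers hearing is unclear, but a shortfall is not shown.
- *A reader might infer that the power figures are wrong.* They reproduce.

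**Conclusion.** The point holds on the text. Two fallback data sets are named for one trigger, a carryover test with no stated level or statistic selects the analysis, and the reason given for expecting no differential carryover is invalid.

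The numerical consequence is conditional on the assumed test. With patient totals and exchangeable measures, overall type I error is about 5.6–7.5% (cycle 1) or 6.4–8.6% (two cycles). The harm is concentrated after a positive test, at about 13–41% or 23–60%. Audiogram-only noise, or a within-patient contrast, brings these down substantially. With a totals test the two fallbacks disagree on significance in about 20–32% of trials with a positive test, which is roughly 1–3% of all null trials. It would be wrong to read the upper conditional figure as the error rate of the plan.

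This should be corrected before analysis. It does not undermine the crossover design.

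**What to change.** Put the same text in 6.1.1 and 6.2, for example: *The crossover mixed model is the primary analysis of hearing. Whatever its result, the between-sequence comparison of the change in 4–8 kHz threshold from pre-cycle 1 to pre-cycle 3 will also be reported, with its 95% confidence interval, as a sensitivity analysis. The two ears will be handled as in the primary analysis. No carryover test will be used to choose between the two.*

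Delete the clause that offers randomised order as the reason. State that 1.2 SD is in units of the SD of that two-cycle change, with 12 patients per group. Since each threshold "will be derived separately for each ear from each audiogram", the sensitivity analysis need only follow whatever the primary model does with ears.

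The cost is a wording change in two sections. Both audiograms are already scheduled, so there are no new visits or data. The downside is that the sensitivity analysis is less precise than the crossover and should be presented as such.
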